### **7.9 End-of-Treatment Visit**

Twenty-eight days ( $\pm 7$  days) after the last dose of trial treatment, patients are expected to return to the trial site to complete all end of treatment assessments as follows:

- Physical (including Site/Organ System Status [includes: General appearance, skin, H/E/E/N/T – Thyroid, Pulmonary, Cardiovascular, Gastrointestinal, Musculoskeletal/Extremities, Genitourinary/Breast, Lymph Nodes, Neurological, and Psychiatric]), including weight
- Vital signs (5-minute sitting blood pressure, pulse, respiratory rate, oxygen saturation, and oral temperature)
- 12-lead ECG
- aPTT and INR or PT
- ECOG performance status assessment
- Clinical laboratory tests (hematology, chemistry panel, thyroid function, and urinalysis)
- Biomarker blood sample
- Pregnancy test (urine or serum) in women of childbearing potential
- Concomitant medications
- Adverse events

### **7.10 Follow-Up Periods**

During the extended safety observation period, all randomized patients will be followed for safety 60 and 90 days ( $\pm 7$  days) after the last dose of study treatment and monitored according to the SOA ([Appendix A](#)).

During the long-term follow-up period, all randomized patients will be followed for OS every 8 weeks ( $\pm 7$  days) during the first year from the 90-day follow-up visit, every 12 weeks ( $\pm 7$  days) during the second year, and every 16 weeks ( $\pm 7$  days) thereafter. The survival follow-up will be conducted until death or study completion, whichever is first, whether or not trial treatment was administered.

For patients who were randomized, but withdrew consent, survival (date of death) will be obtained by use of publicly available information.

The Investigator (or designee) will acquire the following information from patients who were randomized:

- Tumor assessment will be repeated every 8 weeks ( $\pm 7$  days) during the study treatment and during the first year from discontinuation of the study treatment, every 12 weeks ( $\pm 7$  days) during the second year, and every 16 weeks ( $\pm 7$  days) thereafter. Tumor assessment will be repeated until study completion, disease progression, death, or receipt of new anti-cancer therapy for patients who were randomized, and not treated or discontinued treatment before disease progression, and do not withdraw consent.
- Subsequent cancer treatments (all randomized patients)
- Any SAEs considered to be related to trial treatment that occur  $>30$  days post last day of trial treatment, follow until resolution
- Date and cause of death (all randomized patients).

### 7.11 Laboratory Assessments

Local laboratories will perform the following laboratory tests, and results will be provided to the Investigator. Blood and urine samples for hematology, chemistry panel, aPTT and INR or PT, thyroid function, and urinalysis will be prepared using standard procedures.

Laboratory panels are defined as follows:

|                       |   |
|-----------------------|---|
| Hematology:           | WBC count with differential, RBC count, hemoglobin, hematocrit, reticulocyte count, and platelet count  |
| Chemistry Panel:      | albumin, ALP, ALT, AST, BUN, calcium, carbon dioxide, chloride, creatinine, glucose, potassium, sodium, total bilirubin, lactate dehydrogenase, and total protein   |
| Coagulation Tests:    | aPTT and INR or PT  |
| Thyroid Function Test | TSH, Free T3, and T4  |
| Urinalysis:           | appearance, color, pH, specific gravity, ketones, protein, glucose, bilirubin, nitrite, urobilinogen, and occult blood (microscopic examination of sediment will be performed only if the results of the urinalysis dipstick evaluation are positive) |
| Pregnancy Test        | Serum or urine pregnancy test for women of child bearing potential  |

Abnormalities in clinical laboratory tests that lead to a change in patient management (ie, dose withhold, requirement for additional medication or monitoring) are considered clinically significant for the purposes of this trial and will be recorded on the AE CRF page. If values meet criteria defining them as serious, they must be reported as SAEs (Section 9.1.2).

### 7.12 Pharmacokinetics

Blood samples for PK with sparse sampling techniques will be obtained on all patients on Arm 1 (including crossover patients). Serum samples will be collected to characterize PK of AM0010 in combination with nivolumab and to explore exposure-safety and exposure-efficacy relationships. Data from these investigations may be evaluated for correlations with response, survival, and safety data.

The PK samples will be drawn pre-dose (AM0010 and nivolumab):

- Day 1 of Cycles 1, 2, 3, 4, and every fourth cycle thereafter (eg, 8, 12, 16, etc.)
- End-of-treatment visit
- Safety observation visits 60 and 90 days after the last dose of study treatment.

For the sample collection during continued-access period, refer Section 3.7 and [Appendix B](#).

Bioanalytical samples collected to measure investigational product concentration will be retained for a maximum of 1 year following the last participant visit for the study.

### **7.13 Immunogenicity (Anti-Drug Antibodies)**

Blood samples for immunogenicity analysis will be obtained on all patients on Arms 1 and 2 (including crossover patients). Samples will be evaluated for development of ADAs by a validated immunoassay.

The ADA samples will be drawn pre-dose (AM0010 and nivolumab):

- Day 1 of Cycles 1, 2, 3, 4, and every fourth cycle thereafter (eg, 8, 12, 16, etc.).
- End-of-treatment visit
- Safety observation visits 60 and 90 days after the last dose of study treatment.

For the sample collection during continued-access period, refer Section 3.7 and [Appendix B](#).

All immunogenicity samples will be retained for a maximum of 15 years after the last participant visit, or for a shorter period if local regulations and Ethical Review Boards (ERBs) allow, at a facility selected by the sponsor. The duration allows the sponsor to respond to future regulatory requests related to the investigational product. Any samples remaining after 15 years will be destroyed.

### **7.14 Biomarkers**

Blood samples for biomarker analysis will be obtained on all patients in Arms 1 and 2. A variety of factors that may impact the immunomodulatory properties and efficacy of AM0010 in combination with nivolumab will be investigated in peripheral blood. Data from these investigations may be evaluated for correlations with response, survival, and safety data.

Biomarker samples will be drawn pre-dose (AM0010 and nivolumab):

- Day 1 of Cycles 1, 2, 3, 5, 7, 9, 11, etc.
- End-of-treatment visit.

All biomarker samples (both tissue and blood) will be retained for a maximum of 15 years after the last participant visit, or for a shorter period if local regulations and ERBs allow, at a facility selected by the sponsor. The duration allows the sponsor to respond to future regulatory requests related to the investigational product. Any samples remaining after 15 years will be destroyed.

## **8.0 REMOVAL AND REPLACEMENT OF PATIENTS**

### **8.1 Removal of Patients**

Patients have the right to withdraw from the trial at any time and for any reason without prejudice to his or her future medical care by the physician or at the institution.

Any patient who withdraws consent to participate in the trial will be removed from the trial immediately upon the date of request. The Investigator will make every effort to contact the patient and perform end-of-treatment procedures. Should a patient (or a legally acceptable representative) request or decide to withdraw from the trial, all efforts will be made to complete and report the observations as thoroughly as possible in addition to follow up for OS. All information should be reported on the applicable CRFs.

The patient who requests to stop trial treatment or has withdrawn from trial treatment because of the Investigator's or Sponsor's concern before completion of the protocol-specified treatment duration will be strongly encouraged to continue the schedule of trial observations, in addition to follow up for OS.

If the patient has withdrawn because of toxicities, the Investigator should arrange for the patient to be followed for a minimum of 90 days or until any drug-related toxicities resolve to grade 1 according to CTCAE Version 4.03, or return to the patients' baseline values, in addition to follow up for OS. All end-of-treatment procedures should be completed for such a patient.

Reasons for removal from investigational product or observation may include:

- Withdrawal of consent
- Administrative decision by the Investigator or Sponsor
- The patient's physician feels it is no longer in their best interest of the patient to continue on treatment
- Require subsequent systemic anticancer therapy
- Pregnancy (report on Pregnancy Notification Worksheet/CRF)
- Ineligibility determined after enrollment
- Significant protocol deviation
- Patient noncompliance
- Adverse event (disease progression is not considered an AE)
- Progression of disease (clinical and/or radiological)
- Lost to follow-up.

The reason for withdrawal, the date of administration of the final trial treatment, and the date of withdrawal should be recorded on the End-of-Treatment CRF.

All randomized patients will be followed for OS every 8 weeks ( $\pm 7$  days) during the first year from the 90-day follow-up visit, every 12 weeks ( $\pm 7$  days) during the second year, and every 16 weeks ( $\pm 7$  days) thereafter. The survival follow-up will be conducted until death or study completion, whichever is first, whether or not trial treatment was administered.

For patients who were randomized, but withdraw consent, survival (date of death) will be obtained by use of publicly available information.

All randomized patients who discontinue trial treatment before disease progression or patients randomized, but not treated, will be followed for PFS every 8 weeks ( $\pm 7$  days) until study completion, disease progression, or death or receipt of new anti-cancer therapy, whichever is first. Scans will include CAPs and head, and will be sent to the central imaging vendor for archiving. If clinical progression is suspected, all relevant clinical documentation is to be submitted to the central imaging vendor for archiving.

The Investigator (or designee) will acquire the following information from patients who were randomized:

- Tumor assessment for all randomized patients who discontinue the trial treatment before disease progression or patients randomized but not treated. Tumor assessment will be repeated until study completion, disease progression, death or receipt of new anti-cancer therapy, whichever is first.
- Subsequent cancer treatments (all randomized patients).
- Any SAEs considered to be related to trial treatment.
- Date and cause of death (all randomized patients).

## **8.2 Replacement of Patients**

Randomized patients who withdraw from the trial will not be replaced.

## 9.0 ADVERSE EVENT REPORTING

### 9.1 Definitions

#### 9.1.1 Adverse Events

An AE is defined as any untoward medical occurrence in a patient or clinical investigation subject administered a pharmaceutical product that does not necessarily have a causal relationship with this treatment. An AE can therefore be any unfavorable and unintended sign (including an abnormal laboratory finding), symptom, or disease temporally associated with the use of a medicinal (investigational) product, whether or not related to the medicinal (investigational) product.

Investigators are responsible for:

- monitoring the safety of patients in this study and for alerting Lilly or its designee to any event that seems unusual, even if this event may be considered an unanticipated benefit to the patient,
- the appropriate medical care of patients during the study,
- documenting their review of each laboratory safety report, and
- following, through an appropriate healthcare option, AEs that are serious or otherwise medically important, considered related to study treatment or the study, or that caused the patient to discontinue study treatment before completing the study. The patient should be followed until the event resolves, stabilizes with appropriate diagnostic evaluation, or is reasonably explained. Frequency of follow-up evaluation is left to the discretion of the investigator.

A worsening of an existing medical condition occurs when a condition present at the time the informed consent form is signed (eg diabetes, migraine headaches, gout) becomes more severe, more frequent, or increases in duration during investigational product treatment.

Abnormal laboratory values should not be reported as an AE, unless they are considered clinically significant by the Investigator; however, any clinical consequences of the abnormality should be reported as an AE. Abnormalities in clinical laboratory tests that lead to a change in patient management (ie, dose schedule reduction or withhold, requirement for additional medication or monitoring) are considered clinically significant for the purposes of this trial and will be recorded on the AE CRF page.

Lack of drug effect is not an AE in clinical studies because the purpose of the clinical study is to establish treatment effect.

Planned surgeries and nonsurgical interventions should not be reported as AEs unless the underlying medical condition has worsened during the course of the study.

If a study patient experiences elevated ALT  $\geq 5 \times$  upper limit of normal (ULN) and elevated total bilirubin  $\geq 2 \times$  ULN, or ALT  $\geq 8 \times$  ULN, liver tests ([Appendix E](#)), including ALT, AST, total bilirubin, direct bilirubin, gamma-glutamyl transferase (GGT), and creatine phosphokinase (CPK), should be repeated within 3 to 5 days to confirm the abnormality and

to determine if it is increasing or decreasing. If the abnormality persists or worsens, clinical and laboratory monitoring should be initiated by the investigator, based on the hepatic monitoring tests ([Appendix E](#)) and in consultation with the Lilly Clinical Research Physician (CRP). Monitoring of ALT, AST, and total bilirubin should continue until levels normalize or return to approximate baseline levels.

### **9.1.2 Serious Adverse Events**

An SAE is any AE from this study that results in 1 of the following outcomes:

- death
- initial or prolonged inpatient hospitalization
- a life-threatening experience (ie, immediate risk of dying)
- persistent or significant disability/incapacity
- congenital anomaly/birth defect
- important medical events that may not be immediately life-threatening or result in death or require hospitalization may be considered serious when, based upon appropriate medical judgment, they may jeopardize the patient and may require intervention to prevent 1 of the other outcomes listed in the definition above.

## **9.2 Suspected Unexpected Serious Adverse Reactions**

Suspected unexpected serious adverse reactions (SUSARs) are serious events that are not listed in the IB and that the investigator identifies as related to study treatment or study procedure. United States 21 Code of Federal Regulations (CFR) 312.32 and Regulation (EU) No. 536/2014 and the associated detailed guidances or national regulatory requirements in participating countries require the reporting of SUSARs. Lilly has procedures that will be followed for the recording and expedited reporting of SUSARs that are consistent with global regulations and associated detailed guidances.

### **9.2.1 Pregnancy**

Pregnancy (during maternal or paternal exposure to study treatment) does not meet the definition of an AE, but should be reported. However, to fulfill regulatory requirements any pregnancy should be reported following the SAE process to collect data on the outcome for both mother and fetus.

The Investigator will inform Lilly within 24 hours of awareness by any study personnel of any case of pregnancy and collect information on any exposure to the study drug(s) during pregnancy (female patient or male patient's partner). An exposure during pregnancy (also referred to as exposure in utero) occurs if a female is or has been found to be pregnant after being exposed to the study drug(s) directly, indirectly, or via her partner (paternal exposure). If any study subject becomes or is found to be pregnant and exposed to investigational product as described above, the Investigator must submit this information to Lilly on a Pregnancy Report Form irrespective of whether an AE has occurred and within 24 hours of

awareness of the pregnancy. The information submitted should include the anticipated date of delivery. Follow-up is conducted to obtain pregnancy outcome information on all exposure during pregnancy reports with an unknown outcome. The Investigator will follow the pregnancy until completion or until pregnancy termination (ie, induced abortion) and then notify Lilly of the outcome. The Investigator will provide this information as a follow-up to the initial Pregnancy Report Form. The reason(s) for an induced abortion should be specified. A report is not created when an ectopic pregnancy report is received since this type of pregnancy is not usually viable. Rather, an SAE case is created with the event of ectopic pregnancy. If the outcome of the pregnancy meets the criteria for immediate classification as an SAE (ie, spontaneous abortion, stillbirth, neonatal death, or congenital anomaly [including that in an aborted fetus, still birth, or neonatal death]), the Investigator should follow the procedures for reporting SAEs. In the case of a live birth, the “normality” of the newborn can be assessed at the time of birth (ie, no minimum follow-up period of a presumably normal infant is required before a Pregnancy Report Form can be completed), and birth information will be provided as a follow-up of the initial Pregnancy Report Form. Case processing at Lilly will be performed as described above for SAE reports. Additional information regarding the exposure during pregnancy may be requested by the Investigator. Further follow-up of birth outcomes will be handled on a case-by-case basis (eg, follow-up on preterm infants to identify developmental delays).

### **9.3 Reporting Procedures for All Adverse Events**

After the ICF is signed, study site personnel will record via electronic case report form (eCRF) the occurrence and nature of each patient’s preexisting conditions, including clinically significant signs and symptoms of the disease under treatment in the study. In addition, study site personnel will record via eCRF any change in the preexisting conditions and any new conditions as AEs. Investigators should record their assessment of the potential relatedness of each AE to study treatment via eCRF.

All AEs, regardless of grade and occurring after obtaining informed consent, observed by the Investigator or reported by the patient (whether or not attributed to investigational product), will be reported on the AE CRF. Please note that disease progression should not be considered an AE but shall be documented on the appropriate CRF.

Medically significant AEs considered to be related to the investigational product by the Investigator or Sponsor will be followed until resolved or considered stable. The Investigator must assign the following attributes: description (concise diagnosis, if available); dates of onset and resolution; severity; assessment of relatedness to investigational product; and action taken. The Investigator may be asked to provide follow-up information, medical records, and extracts from medical records or CRFs.

The SAE reporting to Lilly or its designee begins after the patient has signed the ICF and has received study treatment. However, if an SAE occurs after signing the ICF, but prior to receiving study treatment, it needs to be reported ONLY if it is considered reasonably

possibly related to study procedure. “Death” as an outcome of an AE may occur and should not be reported as an AE, but the cause of death should be reported on the AE eCRF.

For the purpose of this study, progression of underlying malignancy is not considered an (S)AE. Hospitalization, prolonged hospitalization, or death due solely to the progression of underlying malignancy will be captured on the AE CRF, but will NOT be reported as an SAE. Clinical symptoms of progression may be reported as AEs if they cannot be determined to be exclusively due to the progression, or if they do not fit the expected pattern of progression for late-stage NSCLC cancer.

The SAEs that are considered related to study drug occurring >30 days after last trial treatment must be reported on both a CRF and on a SAE Report Form (with an autopsy report if available).

Investigators are not obligated to actively seek AEs or SAEs in patients once they have discontinued study. However, if the investigator learns of any SAE, including a death, at any time after a patient has been discontinued from the study, and he/she considers the event reasonably possibly related to the study treatment or study participation, the investigator must promptly notify Lilly or designee.

Lilly will periodically review evolving aggregate safety data within the study by appropriate methods.

If it is deemed to be in the best interest of the patient to start a new anti-cancer treatment prior to the follow-up visit, the visit duration may be shortened. In this case, the follow-up assessments should be completed prior to the initiation of the new therapy. If an anti-tumor treatment is initiated within 90 days of the last dose of trial treatment, the start date of this treatment should be documented on the appropriate CRF.

The Investigator must notify the IRB of SAEs occurring at the site and other AE reports received from Lilly/designee in accordance with local procedures/site IRB policies.

It will be left to the Investigator’s clinical judgment whether or not an AE is of sufficient severity to require the patient’s removal from treatment. A patient may also voluntarily withdraw from treatment due to what he or she perceives as an intolerable AE. If either of these occurs, the patient must undergo an end-of-treatment assessment and be given appropriate care under medical supervision until symptoms cease or the condition becomes stable. If the patient is permanently withdrawn from the trial or investigational product due to an SAE, this information must be included in either the initial or follow-up SAE Report Form or the End-of-Treatment CRF.

Study site personnel must report any treatment discontinuations that result from AEs to Lilly or its designee via the eCRF, clarifying, if possible, the circumstances leading to the discontinuation of treatment.

The trial will use the Common Terminology Criteria for grading AEs that are experienced by research patients. If the AE is not specified in the NCI-CTCAE v4.03 the severity will be assessed on the following scale with appropriate clinical definitions:

1 = mild, 2 = moderate, 3 = severe, 4 = life-threatening, 5 = fatal.

The investigator will interpret and document whether or not an AE has a reasonable possibility of being related to study treatment or a study procedure, taking into account the disease, concomitant treatments, or pathologies.

The relationship of the AE to the investigational product will be assessed by means of the question: ‘Is there a reasonable possibility that the event may have been caused by the investigational product?’ Answer Yes or No.

Determination of expectedness will be based on the contents of the Investigator’s Brochure.

The Medical Dictionary for Regulatory Activities (MedDRA) will be used to classify the events.

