In the study in non-squamous NSCLC, the median OS was 12.2 months among patients in the nivolumab group as compared to 9.4 months among the 290 patients in the docetaxel group; HR 0.72, p=0.002. The 18-month OS rate was 39% with nivolumab vs 12% with docetaxel. Although the progression-free survival (PFS) did not favor nivolumab over docetaxel (median 2.3 months and 4.2 months, respectively), the rate of PFS at 1 year was higher with nivolumab than with docetaxel (19% and 8% respectively). Nivolumab was associated with greater efficacy than docetaxel across all end points in subgroups defined according to pre-specified levels of tumor-membrane expression ( $\geq 1\%$ ,  $\geq 5\%$ , and  $\geq 10\%$ ) of PD-L1. Treatment-related adverse events (TRAEs) of Grade 3 or 4 were reported in 10% of the patients in the nivolumab group (Borghaei, Paz-Ares et al. 2015).

Patients with advanced squamous-cell NSCLC who have disease progression during or after first-line chemotherapy were treated in a Phase 3 randomized study evaluating the efficacy and safety of nivolumab as compared with docetaxel in this patient population ((Brahmer, Reckamp et al. 2015). The OS was 9.2 months with nivolumab vs 6.0 months with docetaxel; HR 0.59,  $p < 0.0001$ . At 1 year, the OS rate was 42% with nivolumab vs 24% with docetaxel. The response rate was 20% with nivolumab vs 9% with docetaxel ( $p = 0.008$ ). The median PFS was 3.5 months with nivolumab vs 2.8 months with docetaxel (HR 0.62,  $p < 0.0001$ ). The expression of the PD-1 ligand was neither prognostic nor predictive of benefit. Treatment-related adverse events of Grade 3 or 4 were reported in 7% of the patients in the nivolumab group as compared with 55% of those in the docetaxel group.

Nivolumab is Food and Drug Administration (FDA)-approved as a single agent for the treatment of patients with metastatic NSCLC with progression on or after platinum-based chemotherapy. Combining AM0010 with nivolumab may present a promising therapeutic combination to address this unmet medical need in patients with advanced NSCLC.

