#### **10.5.6 Adverse Events**

Adverse events will be analyzed in terms of treatment-emergent AEs defined to be any AEs that begin or worsen in intensity after trial drug initiation through 30 days after the last dose of trial drug. All AEs will be coded based on MedDRA terms.

Descriptive statistics of safety will be presented using NCI-CTCAE version 4.03 by treatment arm. All treatment emergent AEs, treatment-related AEs, SAEs, treatment-related SAEs, and AEs leading to discontinuation from the trial treatments will be tabulated using the worst grade per NCI-CTCAE v4.03 criteria by system organ class and preferred term. Additional summaries include AEs by intensity (Grade 1 to 4 or/and Grades 3 and 4).

Non-treatment emergent AEs arising from screening procedures or occurring more than 30 days after the last dose will be summarized or listed.

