- c A fresh tissue biopsy is only required if no archival tissue is available within 60 days of informed consent or unless approved by the Medical Monitor.
- d Mandatory tumor tissue sample for biomarker research should be submitted once the patient is enrolled (preferably from the same block used for PD-L1 testing).
- e ADA and PK samples will be collected on Day 1 of Cycles 1, 2, 3, 4, every fourth cycle thereafter, and at end-of-treatment visit, and at the follow-up visits 60 and 90 days after the last dose of study treatment.
- f Biomarker samples will be collected on Day 1 of Cycles 1, 2, 3, 5, 7, 9, 11, etc. and end-of-treatment visits. Specific biomarker blood collection tubes may vary by time point. See the Lab Manual for details.

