#### **6.7.4. Crossover Patients**

Patients in Arm 2 (nivolumab) who crossover to Arm 1 (AM0010 in combination with nivolumab) following documented disease progression will be analyzed accordingly if data warrants.

For patients who crossover to Arm 1 after documented disease progression on nivolumab, time to progression while on nivolumab and time to progression following progression will be estimated, where the time to progression following crossover is defined as the time from time of crossover to the earliest documented disease progression. The last available tumor assessment before crossover will serve as the baseline for disease assessment post crossover. If the number of events permits, time to progression before and after crossover will be summarized descriptively using the Kaplan-Meier method

Patients who crossover to the AM0010 in combination with nivolumab are censored at time of crossover (i.e., AEs occurring during treatment with AM0010+nivolumab are excluded for control arm (nivolumab) patients). An exploratory safety analysis may be conducted for the crossover patients including all adverse events starting from the date of first dose of AM0010+nivolumab.

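### After a treatment switch the by-arm TEAE windows are unequal: closed at crossover for Arm 2, left open after any other new anti-cancer therapy

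*Protocol*

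**What the plan says.** **TEAE window.** Protocol 10.5.6 counts events that begin or worsen after the first dose "through 30 days after the last dose of trial drug". SAP 6.6.2 runs the window to 30 days after treatment discontinuation and sets no time limit for events that are both serious and related. Neither definition mentions the start of another anti-cancer therapy.

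**Crossover.** At progression, Arm 1 patients leave the treatment period, while Arm 2 patients may move to AM0010 plus nivolumab (protocol 3.0). Protocol 7.8.1 allows at most 21 days between the progression scan and crossover. SAP 6.7.4 censors these patients for safety at crossover: "AEs occurring during treatment with AM0010+nivolumab are excluded for control arm (nivolumab) patients".

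**New therapy and follow-up.** Protocol 9.3 covers the case where it is in the patient's interest "to start a new anti-cancer treatment prior to the follow-up visit, the visit duration may be shortened", and continues: "In this case, the follow-up assessments should be completed prior to the initiation of the new therapy". If the new treatment starts within 90 days of the last dose, "the start date of this treatment should be documented on the appropriate CRF". Protocol 7.10 says that "all randomized patients will be followed for safety 60 and 90 days" after the last dose, with no exception; the synopsis and Sections 3.5 and 7.2 say the same. Appendix A, footnote e, schedules PK and anti-drug antibody (ADA) samples "at the follow-up visits 60 and 90 days after the last dose of study treatment".

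**The concern.** Safety is a secondary objective and is tabulated by arm. A reader will compare the two columns as if the windows were the same, and after a switch they are not. An Arm 2 patient who crosses over stops contributing events when AM0010 starts. An Arm 1 patient who progresses can only move to a non-study therapy, and the window stays open to day 30 whatever that therapy is. Its early toxicity then appears in the Arm 1 column as a TEAE of AM0010 plus nivolumab.

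The plan does cut efficacy data at a new therapy. ORR counts responses only up to subsequent anti-cancer therapy (SAP 6.5.2.1), and PFS is censored at the last adequate assessment before it (SAP Table JZGD.6.1, rule 8). Safety has no matching rule except for crossover. With about 25 patients per arm and no data monitoring committee (protocol 6.4.5), a few misattributed patients would be visible in the tables.

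A separate problem is that 9.3 does not say which visit it means. Section 3.5 uses follow-up for the 28 days before the end-of-treatment visit, whereas Appendix A uses it for the day-60 and day-90 visits.

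**Working it through.** The plan states no figure on this point, so there is none to reproduce.

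**1. The rules side by side**

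| Patient | What ends the main TEAE window |
|---|---|
| Either arm, no new therapy | Day 30 |
| Arm 1, any new anti-cancer therapy | Day 30; the new therapy is ignored |
| Arm 2, crosses over | Crossover |
| Arm 2, other new therapy without crossover | Day 30; the new therapy is ignored |

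The imbalance is in the SAP text itself and does not depend on how sites behave.

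**2. Days of the window exposed to the new therapy**

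If the new therapy starts t days after the last dose, the exposed days are max(0, 30 − t):
- t = 7: 23 days
- t = 14: 16 days
- t = 21: 9 days
- t = 28: 2 days
- t = 30 or later: none

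**3. Illustrative size**

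Inputs, which are assumptions and not in the documents:
- f, the share of an arm that starts a new therapy: 10% to 40%
- t, the start day: 14 or 21
- q, the chance over 30 days that such a patient has a first event not already counted: 20% to 50%

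With a constant hazard, the shift in that arm's any-TEAE rate is f × [1 − (1 − q)^((30 − t)/30)]. Patients are this times 25, the planned arm size (protocol 10.3), so one patient is 1/25 = 4 points.

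- Lowest: 0.10 × [1 − 0.8^(9/30)] = 0.10 × 0.0648 = 0.6 points, or 0.16 patients.
- An intermediate case: 0.20 × [1 − 0.8^(16/30)] = 0.20 × 0.1122 = 2.2 points, or 0.56 patients.
- Highest: 0.40 × [1 − 0.5^(16/30)] = 0.40 × 0.3090 = 12.4 points, or 3.09 patients.

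This is the shift within one arm. Where Arm 2 patients take other therapies early without crossing over, their column shifts too and part of the difference cancels. The distortion between arms grows with the share of Arm 2 switches that are crossovers, which is unknown.

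**4. Do the day-60 and day-90 visits matter to these rates?**

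With the 7-day tolerance, the earliest day-60 visit is 60 − 7 = day 53 and the earliest day-90 visit is 90 − 7 = day 83. Both fall after day 30. Only the end-of-treatment visit, 28 ± 7 = days 21 to 35, overlaps the window. Keeping, moving or omitting the later visits therefore cannot change the main TEAE rates, apart from late serious related events under the SAP definition. What those visits can affect is the day-60 and day-90 PK and ADA samples and the separate reporting of events after day 30.

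**The case against.** The best defence is that a fixed 30-day all-cause window is a legitimate design choice. Investigators assess relatedness with concomitant treatments in mind (protocol 9.3), and SAP 6.6.2 repeats its main summaries for related events, so toxicity of a later drug can be separated there. The analyses are descriptive by arm, and no formal safety test depends on the window.

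Much of this stands, and it limits the severity. It does not remove the point. The window is not in fact fixed, because SAP 6.7.4 already cuts it for one kind of switch in one arm. The related-event tables help only in part: the all-cause tables are still produced, the trial is open-label, and protocol 13.3 stops recording concomitant medication after a new therapy except for AM0010-related events, which makes later attribution harder.

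Four stronger readings are tempting, and the documents do not support them:

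- **Arm 1 event rates depend on whether a site follows 9.3 or 7.10.** Section 9.3 does not say that event collection stops, and it asks for all events after consent to be recorded. The visits in conflict lie outside the 30-day window.
- **The problem is confined to Arm 1.** Crossover is optional, and Arm 2 patients who take another therapy are affected in the same way.
- **The shift could reach 26 points.** That figure is 12 × 0.55 / 25 = 26.4%, with 12 switching patients assumed. The 55% comes from protocol 1.1, which reports treatment-related Grade 3 or 4 events in "7% of the patients in the nivolumab group as compared with 55% of those in the docetaxel group". That is a study-level rate with no 30-day time frame, and patients who already had a Grade 3 or higher TEAE would not be counted again.
- **Day-60 and day-90 samples will be lost.** Section 9.3 speaks of completing assessments earlier and does not say that they are omitted.

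**Conclusion.** The point holds as an asymmetry in the analysis rules. Arm 2 patients lose the rest of their window at crossover, while every other switch, including every switch after progression in Arm 1, leaves it open to another drug's toxicity.

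The size cannot be derived from the documents. The illustration gives about 0.6 to 12.4 points on one arm's any-TEAE rate, resting on the assumed share of switchers, start day, event probability and constant hazard. If most switchers have already had some TEAE, the any-TEAE shift will sit near the low end; single preferred terms and Grade 3 or higher rates have more room to move.

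This should be fixed, but it ranks low among changes of that kind: nothing formal is tested, and the related-event tables soften it. The conflict between 9.3 and the visit schedule is real but separate, and it does not act on the main 30-day rates through the day-60 and day-90 visits.

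**What to change.** In protocol 10.5.6 and SAP 6.6.2, use one rule for both arms:

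- End the window for the main by-arm TEAE tables on the day before the first dose of any new anti-cancer therapy, crossover treatment included. SAP 6.5.5.2 already uses this date convention for its OS sensitivity analysis.
- Keep the SAP's open-ended provision for serious related events, use the same wording in the protocol, and state how it applies to crossover patients.
- List or tabulate later events separately by arm.

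The cost is wording and one programming rule, because 9.3 already has the start date recorded. The downside is that delayed non-serious study-drug events after a switch move from the main tables to the separate one.

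Separately, reconcile 9.3 with the synopsis, Sections 3.5, 7.2 and 7.10, and Appendix A. State which visit 9.3 covers, whether event collection continues after a new therapy starts, and whether the day-60 and day-90 PK and ADA samples are still taken. Which follow-up rule applies is for the sponsor to decide. The cost is protocol wording, plus any later visits that the chosen rule requires.
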